10 STUDY DRUG

Please see the Study Reference Manual for additional information on Study Drug supplies, packaging, storage, dispensation, and accountability.

10.1 FORMULATION, PACKAGING AND LABELING

The Study Drug in this trial is nalbuphine HCl ER tablets. Nalbuphine HCl ER tablets are white to off white film-coated round tablet containing either 30 mg or 60 mg nalbuphine HCl.

All study medication will be supplied by the Sponsor. Following confirmation of eligibility to start the Treatment Period, the patient will receive bottles of study drug tablets containing 60 tablets each. Bottles will be labeled with at minimum: contents, storage conditions, expiration date, clinical trial statement, and the name and lot number of the study drug Sponsor (Trevi Therapeutics).

10.2 SHIPPING, STORAGE AND HANDLING

The Investigator will ensure that the Study Drug is stored and dispensed in accordance with ICH QE6(R1) (Guideline for Good Clinical Practice) and EU Clinical Trial Directive and Annex13 regulations concerning the storage and administration of investigational drugs.

Nalbuphine HCl ER tablets and placebo tablets should be stored at 20°C-25°C (68°F-77°F) with excursions permitted between 15°C and 30°C (59° to 86°F). The storage conditions were established following ICH Q1A(R2) (Stability testing of new drug substances and drug product) and the CHMP Guideline CPMP/QWP/122/02, rev 1 corr CHMP Guideline (Stability Testing of existing active substances and related Finished products) for assessment and provision of appropriate labelling and storage conditions.

The Study Drug will be stored away from any extreme conditions of temperature, light, or humidity as an additional precaution

In the EU, the investigational medicinal products will remain under the control of the Sponsor until after completion of a two-step procedure: certification by the Qualified Person; and release by the Sponsor for use in a clinical trial following fulfillment of the requirements of Article 9 (Commencement of a clinical trial) of Directive 2001/20/EC. Both steps will be recorded and retained in the relevant trial files held by or on behalf of the Sponsor.

10.3 UNBLINDING

Not applicable. This is an open-label study.

10.4 DRUG ACCOUNTABILITY

The Investigator must ensure that all drug supplies are kept in a secure locked area with access limited to those authorized by the Investigator. The Investigator must maintain accurate records of the receipt of all Study Drug shipped by the Sponsor or the Sponsor's representative, including but not limited to the date received, lot number, expiration date, amount received, and the disposition of all Study Drug. Current dispensing records will also be maintained including the date and amount of drug dispensed and the patient receiving the drug. All remaining drug not required by regulations to be held by the clinical facility will be returned to the depot for destruction at the end of the study.

11 PREMATURE DISCONTINUATION OF STUDY DRUG TREATMENT

Patients who complete Study Drug treatment through the End of Treatment Visit (TV14) are considered to have completed Study Drug treatment (even if some doses have been missed). Patients who discontinue Study Drug treatment, **for reasons other than withdrawal of consent**, prior to the End of Treatment visit (TV14) will be considered to have prematurely discontinued Study Drug treatment and will be asked to complete the following visits:

- End of Treatment Visit (TV14) *regardless of where they are in the study visit schedule
- Washout and Safety Follow-up Period Visit
- Premature Discontinuation of Study Drug Telephone Contact Visit

11.1 PREMATURE DISCONTINUATION OF STUDY DRUG TREATMENT ASSOCIATED WITH FAILURE-TO-IMPROVE CRITERIA

Patients, who meet failure-to-improve criteria during the conduct of the study, will stop taking study medication. The Failure-to-Improve criteria are as follows:

Beginning on TV 3, and at every subsequent Treatment Visit, patients with a Worst Itch NRS equal to or greater than (\geq) the Worst Itch NRS at Visit 1a (or at Visit 1b in the case of patients who require the Observation Visit period) will be discontinued from study drug. Patients discontinued from study drug are to undergo the End of Treatment Visit (TV14), the Washout/Safety Follow-up Period assessment in two weeks, and receive a follow-up Telephone Contact 30 days following end of study drug dosing for final safety assessment.

Below are examples of the assessment of Failure to Improve Criteria:

Examples	Visit	Worst Itch NRS	Worst Itch NRS Lower/Higher or no change from V1a/1b	Failure-to-improve met for that visit?	Next Steps
Visit 1a (or Visit 1b)		5	--	--	--
Ex #1	TV3	5	No Change	Yes	Discontinue study drug
Ex #2	TV3	4	Lower	No	Maintain patient on treatment
Ex #3	TV3	6	Higher	Yes	Discontinue study drug

11.2 PREMATURE DISCONTINUATION OF STUDY DRUG TREATMENT FOR REASONS OTHER THAN FAILURE-TO-IMPROVE

Patients who complete Study Drug treatment (as defined in [Section 11](#)) are considered to have completed Study Drug treatment including those that were followed in the Observation Period prior to receiving Study Drug treatment. Patients discontinuing Study Drug treatment prior to the maximum allowable number of Treatment Weeks (based on their entry into the study at either Visit 1a or Visit 1b) will also be considered to have prematurely discontinued Study Drug treatment. Patients removed from the study after enrollment and who have received a dose of study drug will not be replaced.

Some reasons for premature discontinuation of Study Drug treatment include:

- Intercurrent Illness
- Any intolerable AE that cannot be ameliorated or safely managed with medical intervention or one that poses undue risk to the patient if Study Drug treatment were continued in the opinion of the Medical Monitor or Investigator.
- ECG changes as summarized in [Section 17.4](#)
- Opioid medication is introduced in anticipation for chronic use of greater than 2 weeks (see [Section 9.7.8](#))
- Any medication prescribed for chronic anti-pruritic use of greater than 2 weeks (see [Section 9.7.6.1](#))
- Development of substance abuse as determined by the Investigator

12 PREMATURE WITHDRAWAL OF PATIENTS FROM THE STUDY

All patients who receive study treatment should remain in the study whenever possible. Reasons for withdrawal of the patient from the study, not just discontinuation of study drug, include:

- Withdrawal of consent for study participation

- Sponsor terminates the study for any reason
- Investigator decision

The Investigator may withdraw any patient from the study if, in the Investigator's opinion, it is not in the patient's best interest to continue on the study.

- Death of the patient

Any patient whose condition significantly changes after entering the study should be carefully evaluated by the Investigator and discussed with the Medical Monitor. Such patients should be withdrawn from the study if continuing would place them at risk or compromise the results of the study.

Patients who prematurely discontinue from the study will be asked to undergo and have completed Early Termination visit procedures and evaluations that may be necessary to ensure that the patient is free of untoward effects and to seek appropriate follow-up for any continuing problems. The date on which the patient is withdrawn from the study and the reason for discontinuation will be recorded on the CRF. Patients who withdraw from the study will not be replaced.

13 WARNINGS AND PRECAUTIONS

Please refer to the accompanying Investigator's Brochure for more details summarizing the safety data on nalbuphine HCl ER tablets. In addition, see the Warnings and Precautions sections of the parenteral nalbuphine HCl package insert for safety-related information. The package insert is contained in the Study Reference Manual.

14 EFFICACY EVALUATIONS

Efficacy measurements will be evaluated as secondary endpoints in this study. The measurements include:

- Worst itch intensity NRS
- Average itch intensity baseline.
- VRS (itchy, burning and stinging)
- ItchyQoL
- MOS Sleep-R
- HADS
- Prurigo Activity Score (PAS)
- Patient Benefit Index, pruritus version (PBI-P)
- Frequency, pattern, and reasons for dose titration
- Frequency and distribution by time on study of patients determined to meet failure-to-improve criteria
- Changes in the PRO measurements during the Washout Period after cessation of treatment of nalbuphine HCl ER tablets

- Time to first use of rescue medications and number of days of use of rescue medications for itching
- To evaluate the daily changes in the Subjective Opiate Withdrawal Scale (SOWS) during the Washout Period after cessation of treatment of nalbuphine HCl ER tablets.

14.1 EXPLORATORY

The potential of nalbuphine HCl ER tablets to impact on the measurement of nerve fiber density (histology) and MOR/KOR density (histology, Western Blot), as well as histological (H&E) in skin biopsies taken during TR03 and the last week on study drug during TR03ext (optional procedures at select sites only).

15 COLLECTION, HANDLING, AND ANALYSIS OF PHARMACOKINETIC BLOOD SAMPLES

15.1 BLOOD SAMPLE COLLECTION

Blood samples will be collected for safety, pharmacokinetic and CYP analysis. At the time of sample collection and processing, study patient information will be anonymized. Only the patient's identification number, assigned by an IVR/IWR system, and a sample barcode aligned to the lab requisition form will be noted on the tube/vial.

See the PPD Laboratory Manual for specimen collection, handling and shipping details.

15.2 CENTRAL LABORATORY

Blood samples, including chemistry, serum pregnancy test, hematology, and urine for urinalysis will be obtained for the study and analyzed at a central laboratory.

Urine pregnancy testing will be conducted at the site.

The serum pregnancy test result will be used to determine the patient's eligibility to continue receiving study treatment should the urine and serum pregnancy test results differ. See [Section 17.5.2.1](#) regarding how pregnancies are to be handled in this study.

15.3 PHARMACOKINETIC SAMPLES

To determine Study Drug content in plasma, blood samples will be collected at various time intervals over the duration of the study.

15.4 PREPARATION, STORAGE, AND HANDLING FOR PHARMACOKINETIC SAMPLES

Immediately after blood sample collection, the tubes will be gently inverted several times to mix the anticoagulant with the blood sample and placed on ice (4 to 8°C) until centrifuged.

The plasma fraction will be separated by centrifugation of the collection tube. It is preferable that a refrigerated (4 to 8°C) centrifuge be used. Centrifugation will be conducted in a manner to yield approximately 2 x1 mL of plasma (e.g., 10 minutes at 1,500 x g). The plasma fraction will be withdrawn by pipette and divided into 2 evenly

proportioned aliquots in polypropylene freezing tubes. All sample collection and freezing tubes will be clearly labeled in a fashion that identifies the patient identification number, the study dose, and the collection date and time.

Labels will be fixed to freezing tubes in a manner that will prevent the label from becoming detached after freezing. All plasma samples will be processed and placed into either a minus 70°C or minus 20°C refrigerator within 1 hour after collection. Tube labels for PK samples will be provided in the central laboratory kits. Each label will contain the study number, patient number, study day of sample, and time of sample. The actual date and time of blood collection, as well as the processing time will be recorded in the patient's source records and/or the CRF.

All plasma samples will be stored frozen (at either -70°C or -20°C) until they are shipped for storage and analysis.

15.5 ANALYTICAL

Plasma samples will be analyzed for Study Drug using a validated liquid chromatography mass spectrometry (LC-MS/MS) method developed at Tandem Lab/s-RTP, Durham, North Carolina. The units for nalbuphine will be in ng/mL. In addition, metabolite concentrations will be assessed in these samples using an exploratory analytical LC-MS/MS method.

Analysis and reporting of results will be conducted according to the current Standard Operating Procedures for bioanalysis at Tandem labs Durham, North Carolina. Details of the sample analysis, including a bioanalytical study report, will be included with the final clinical study report.

16 TISSUE SAMPLES AND HISTOLOGY

At selected sites only, up to three 3 mm punch skin biopsy samples (optional) will be obtained at Visit 1a/1b and the End of Treatment Visit (TV14).

- A 3x3 mm punch skin biopsy is taken from an itchy region which will be fixed in formalin and then paraffin for routine histology (H&E) and immunohistochemical examination of inflammatory cells and pro-inflammatory mediators.
- For the other two 3x3 mm punch skin biopsy samples taken from an itchy region,
 - One sample will be fixed in 4% paraformaldehyde for 2 h to 5 days, and then kept in 5% sucrose overnight, buffered in 10% and 20% sucrose and after 6 h stored in liquid nitrogen. This tissue will serve for the determination of the nerve fiber density.
 - One sample will be used for RNA and protein extraction for the quantification of MOR/KOR by PCR and western blot.

Analysis will be performed at the University of Munster, Munster, Germany.

See the Study Reference Manual and the Laboratory Manual for specimen collection, handling and shipping details.

17 SAFETY EVALUATIONS

Safety evaluations will include physical examination findings, changes in vital signs and ECGs (locally and centrally read), findings from central laboratory studies and the incidence of AEs

17.1 PHYSICAL EXAMINATION

A complete physical examination will be performed at the Screening Visit and subsequently according to the Schedule of Events ([Appendix 1](#)). Physical examinations may be performed by physicians or mid-level providers, such as advanced practice nurses and physician assistants, if they are appropriately licensed and credentialed to perform these examinations in accordance with local requirements and/or regulations. Any clinically significant worsening after the start of Study Drug treatment will be reported as an AE. Clinically significant findings observed prior to start of Study Drug treatment will be recorded as part of the medical history.

17.2 VITAL SIGN MEASUREMENTS

Blood pressure and HR will be taken while sitting or semi-recumbent/recumbent for at least 5 minutes. Temperature may be taken by any standard method (e.g., oral, tympanic, rectal, etc.), but the method must be recorded.

Vital signs (BP, HR, RR, body temperature, and weight) will be obtained according to the Schedule of Events ([Appendix 1](#)). The height, weight and BMI will be recorded only on Visit 1a.

17.3 LABORATORY EVALUATIONS

A complete series of laboratory evaluations (including hematology, serum chemistry, serum pregnancy and urine pregnancy (both if applicable) and urinalysis) will be obtained according to the Schedule of Events ([Appendix 1](#)). The required clinical laboratory tests are listed in [Appendix 3](#).

Clinically-significant worsening in laboratory findings following start of Study Drug treatment will be recorded as AEs and these will be repeated for verification. Clinically-significant findings noted prior to the start of Study Drug treatment will be recorded as Medical History. The recorded AE will indicate the underlying abnormality or diagnosis as opposed to the observed deviation in laboratory results if the diagnosis is known (e.g. “acute Hepatitis A” is preferable to “ALT increased”).

Additional tests and other evaluations required to establish the significance or etiology of an abnormal result or to monitor the course of an AE will be obtained when clinically indicated. In particular, if a clinically significant abnormal result is observed that is not resolved by the final study visit, tests will be repeated to document resolution or stability of the abnormality.

17.4 ELECTROCARDIOGRAM

A standard 12-lead ECG will be obtained according to the Schedule of Events ([Appendix 1](#)); see the Study Reference Manual for ECG procedures. Electrocardiograms will be read locally by the Principal Investigator for clinical significance and centrally for ECG intervals (PR, RR, QRS, QT, and QTcF using nomogram table), rate, rhythm, and other

clinically significant abnormalities such as left ventricular hypertrophy, pathological Q-waves, etc. Clinically-significant worsening in ECG findings following start of Study Drug treatment will be recorded as AEs. Clinically-significant findings noted prior to the start of Study Drug treatment will be recorded as Medical History.

If a patient develops a QTcF >500ms, associated with an increase from baseline of >60ms, the ECG will be repeated at least 30min later. If these parameters are confirmed on the second ECG by the Core ECG laboratory, the patient will be discontinued from the study.

During the conduct of the trial, if a patient develops any other cardiovascular events noted as part of the exclusion criteria, the cardiovascular assessments in [Appendix 5](#) are to be completed. See [Section 17.5](#) Adverse Events for the handling and follow-up of Adverse Events.

17.5 ADVERSE EVENTS

Adverse events will be recorded starting with the signing of the first informed consent. All AEs will be collected through the Washout and Safety follow up visit (or Early Termination Visit). Adverse events that have not been directly reported to the Investigator will be promptly conveyed to the Investigator by the study staff. Investigators will additionally review any AE source documents and the patient's medical records, on a regular basis during the course of the study; including all study visits.

Following the Washout and Safety follow up visit (or Early Termination Visit), all unresolved AEs that were reported by the Investigator to be probably drug related should be followed by the Investigator until the events are resolved, the patient is lost to follow-up, or the adverse event has stabilized.

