9.6.5 Washout and Safety Follow-Up Period

All patients who received Treatment, but did not withdraw consent, will have a 2-week Washout and Safety Follow-Up Period following TV14. During this visit, the PRO questionnaires (paper versions) must be administered at the study site under the supervision of and by trained study staff, strictly adhering to PRO Administration Instructions (see Study Reference Manual). Please see the Schedule of Events in [Appendix 1](#) for details of the Washout and Safety Follow-Up Period assessments. Additional information for this visit is provided below.

For patients who entered the Treatment Period at Visit 1a, the Washout and Safety Follow-Up Period Visit would take place during week 53, post TV14. However, for a patient who enters the Treatment Period at Visit 1b, the Washout and Safety Follow-up Period Visit will take place 14 days (plus the visit window) post TV14.

For patients who met Failure-to-Improve criteria or who discontinue treatment for other reasons (see [Section 11.1](#)), this visit is to take place 14 days (+ 7 days) after TV14.

The following procedures are to take place at this visit:

- obtain vital signs
- perform 12-Lead ECG after at least 5 minutes in a supine position (See the Study Reference Manual for ECG procedures, [Section 17.4](#) Electrocardiograms for the handling of Cardiovascular adverse events)
- perform brief neurological assessment
- collect blood for central laboratory measurements and PK
- administer PRO measurements (paper versions):
 - Worst itch NRS
 - Average itch intensity NRS
 - VRS
 - ItchyQoL
 - MOS Sleep-R
 - HADS

The PRO questionnaires must be administered at the study site under the supervision of and by trained study staff, strictly adhering to PRO Administration Instructions (see Study Reference Manual).

- AEs and concomitant medications (including rescue medications) will be recorded
- collect the Rescue Medication Log from the patient at this visit
- retrieve any remaining study drug not previously returned by the patient
- retrieve the 14 day SOWS packet

For patients who prematurely discontinued study medication for reasons other than withdrawal of consent, schedule the Premature Discontinuation of Study Drug Follow-up Telephone Contact visit.

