17.5.4 Definition of Relationship to Study Medication

Association or relatedness to the study medication will be graded as either “probably,” “possibly,” or “unlikely.” Determination of relatedness includes:

PROBABLY – The AE:

- follows a reasonable temporal sequence from drug administration;
- abates upon discontinuation of the drug;
- cannot be reasonably explained by the known characteristics of the patient’s clinical state.

POSSIBLY – The AE:

- follows a reasonable temporal sequence from drug administration;
- could have been produced by the patient’s clinical state or by other modes of therapy administered to the patient.

UNLIKELY – The AE:

- does not follow a reasonable temporal sequence from drug administration;
- is readily explained by the patient’s clinical state or by other modes of therapy administered to the patient.

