19.9.2 Adverse Events

All treatment emergent AEs (TEAE) will be summarized overall and for each body system and preferred term by treatment group, relationship to study medication, and severity. For tabulations by severity, only a patient's most severe event within the category (e.g., overall, body system, or preferred term) will be counted. Adverse events will be dichotomized into "related" (probably and possibly) and "unrelated" (unlikely). "Treatment-emergent" will be defined as starting or worsening after the first dose of study drug. If the start date is missing, the event is assumed to be treatment emergent. All SAEs will be tabulated as well.

Although nalbuphine is not a controlled substance in the United States, adverse events of special interest that suggest a possible addiction or abuse potential or withdrawal will be specifically analyzed to screen for these effects. The list of MedDRA preferred terms for adverse events of special interest will be described in the Statistical Analysis Plan.

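### Section 17.5 states a follow-up-to-outcome duty only for AEs graded probably related, so unresolved possibly related AEs, some non-abating AEs and some SAEs have none, mainly in treatment completers

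*Protocol*

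**What the plan says.** Section 17.5 sets the end of general AE collection: "All AEs will be collected through the Washout and Safety follow up visit (or Early Termination Visit)". Beyond that visit, "all unresolved AEs that were reported by the Investigator to be probably drug related should be followed by the Investigator", with three endpoints: resolution, loss to follow-up, or stabilisation.

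Section 17.5.4 defines three causality grades.

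- *Probably* lists a reasonable time sequence, that the event "abates upon discontinuation of the drug", and no reasonable explanation in the patient's clinical state.
- *Possibly* lists a reasonable time sequence and that the event "could have been produced by the patient’s clinical state or by other modes of therapy". It has no abatement item.
- *Unlikely* lists an implausible time sequence and a ready alternative explanation.

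In Section 19.9.2, the sentence opening "Adverse events will be dichotomized into" groups *probably* and *possibly* as related and leaves *unlikely* as unrelated. Section 17.5.2 gives SAEs the same reporting period as other AEs and states no separate rule for following them to outcome.

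Section 9.6.5 says that treated patients who did not withdraw consent "will have a 2-week Washout and Safety Follow-Up Period following TV14".

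**The concern.** The primary objective is safety and tolerability over up to 50 weeks on drug. In such a study, the events whose outcome matters most are those that persist after the drug is stopped. Section 17.5 ties the follow-up duty to the one grade whose definition includes improvement off drug. Other things being equal, the less reversible an event is, the weaker its claim to follow-up.

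The protocol also treats *possibly* related events as drug related when it tabulates them, yet states no duty in 17.5 to learn how they end. At stake are the patients who carry such events out of the study and the description of how those events resolve.

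**Working it through.** No arithmetic applies: the protocol gives no event counts, durations or expected rates. The check is to take each kind of event unresolved at the Washout visit and see which grade it can carry and which duty attaches to it under 17.5.

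| Event unresolved at the Washout visit | Grade under 17.5.4, read literally | Related in 19.9.2? | Duty stated in 17.5? |
|---|---|---|---|
| Lessened off drug, no alternative cause | *Probably* | Yes | Yes |
| Not lessened, graded *probably* while on drug and not re-graded | *Probably* stands; no section requires revision | Yes | Yes |
| Plausible timing, alternative cause possible | *Possibly* | Yes | No |
| Not lessened, plausible timing, no alternative cause | Fits none of the three as written | Undefined | No |
| SAE graded *possibly* | *Possibly* | Yes | No |
| SAE graded *unlikely* | *Unlikely* | No | No |

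The third row is the firmest: it needs no assumption about how the *probably* items are combined. The fourth depends on reading all three items as required. Section 17.5.4 introduces the lists only as what the determination includes, so a site could read them more loosely.

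Events suggesting withdrawal, which 19.9.2 singles out for specific analysis, illustrate the point. They arise because the drug has stopped, so the abatement item cannot sensibly be applied to them.

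Next, what other sections add whatever the grade:

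- **Section 17.3.** The laboratory rule reads: "if a clinically significant abnormal result is observed that is not resolved by the final study visit, tests will be repeated". Its aim is to show that the finding has cleared or is stable. The same section allows further evaluations to monitor the course of any AE when clinically indicated. The first covers laboratory results only; the second is discretionary and has no stated endpoint.
- **Section 9.6.6.** Patients who stop drug prematurely, other than by withdrawing consent, get one telephone contact at 30 days (+2 weeks). It records AEs since the Washout visit. It is a single call, and completers do not receive it. It also records AEs after the point at which 17.5 ends collection.
- **Section 12.** Patients leaving the study early are asked to undergo evaluations and seek follow-up for continuing problems. No endpoint is stated.
- **Section 17.4.** Handling and follow-up of cardiovascular AEs are referred back to 17.5, so this adds nothing.

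For a patient who completes treatment, what remains is laboratory re-testing and the clinically-indicated wording in 17.3. A non-laboratory *possibly* related AE, or a *possibly* related SAE, has no stated duty to be followed to outcome.

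**The case against.** Much can be said for the plan.

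- **Abating is not resolving.** A reader might infer that the rule cancels itself, since an unresolved event cannot have abated. It does not follow: an event that has lessened but persists can be *probably* related and unresolved at once, and is followed.
- **Timing of the grade.** Section 17.5 refers to events already reported as *probably* related. An event may be graded during treatment, before any withdrawal of drug, and nothing requires a later downgrade. A reader might infer that no non-abating related event is ever followed. That holds only if the grade is always reassessed off drug and every item is mandatory; given both, it restates the definition and measures nothing.
- **Non-abating does not mean *possibly*.** A reader might suppose such events must fall into *possibly*. That grade lists a plausible alternative cause, so an event without one does not fit there either.
- **The sections can all be obeyed together.** A reader might see a contradiction between 17.5, 17.3 and 19.9.2. But 19.9.2 is a tabulation rule, 17.3 adds a duty, and 17.5 does not forbid following other events.
- **No planned table is affected.** AEs of every grade are collected through the Washout or Early Termination visit, and 19.9.2 tabulates by body system, preferred term, relationship and severity, not by duration or outcome.

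All five points stand and limit the finding. None supplies a follow-up duty for *possibly* related AEs, or for SAEs outside *probably*, in patients who complete treatment.

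**Conclusion.** The point holds as a gap in the stated follow-up duty. Section 17.5 obliges follow-up to outcome only for unresolved *probably* related AEs. *Possibly* related AEs and SAEs not graded *probably* are outside it; non-abating events may be outside it, depending on how 17.5.4 is read and when the grade is given. Completers have the least cover.

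The number of events affected cannot be estimated from the document. The ceiling is the enrolled population, about 60 patients (Section 19.10). A reader might infer that the incidence or relatedness results are biased; the document does not support that, because those counts close at the Washout or Early Termination visit for every grade. What is lost is the outcome of persistent, possibly related events and assured follow-up of the patients who have them.

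This rests on taking 17.5 as the full statement of the duty beyond the partial provisions set out above. It is a modest defect, worth correcting because the change is small and serves patient safety.

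**What to change.** Reword the second paragraph of Section 17.5 so that the duty covers every unresolved AE that the protocol itself calls related (*probably* or *possibly*) and any unresolved SAE whatever its grade, with the existing endpoints: resolved, stabilised or lost to follow-up.

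Then reconcile the neighbouring text:

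- Section 17.5.4 should say whether every listed item is needed for a grade, so that a non-abating event with no alternative cause has one, and whether the grade is revisited after the drug is stopped.
- Sections 17.3, 9.6.6 and 12 should refer to the same rule, and the end of AE collection in 17.5 should agree with the later telephone contact in 9.6.6.

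The core change is one sentence. It adds no scheduled visit and alters no planned incidence or relatedness table. The cost is a few extra follow-up contacts in a study of at most about 60 patients.
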